9.3.7 Primary Endpoint(s) Analysis

The primary endpoint will be analysed following the estimands strategy for continuous endpoints described in Section 9.3.6.2. The confirmatory 1-sided (superiority) hypothesis, described in Section 9.1, will be tested for delgocitinib cream versus alitretinoin capsules based on the primary analysis for the primary estimand.

9.3.8 Secondary Endpoint(s) Analysis

The confirmatory hypotheses for key secondary endpoints, presented in Section 9.1. will be tested based on the primary analyses for the primary estimand strategies described in Sections 9.3.6.2, 9.3.6.3, and 9.3.6.4.

Table 9-3 provides an overview of the primary statistical analysis of the key secondary efficacy endpoints related to the primary and supplementary estimands. For further details, including sensitivity analysis, refer to Section 9.3.6.

Table 9-3 Overview of the Primary Statistical Analysis of the Key Secondary Efficacy Endpoints Related to the Primary and Supplementary Estimands

Key secondary	Type of	Primary estimand		First Suj	oplementary estimand	Second Supplementary estimand	
endpoints	endpoint	Strategy to handle IEs	Handling of missing data and data collected after IE	Strategy to handle IEs	Handling of missing data	Strategy to handle IEs	Handling of missing data
HECSI-90 at Week 12	Binary	Composite	Non-response	Pandemic	Independent of the	Treatment	Independent of the
IGA-CHE TS at Week 12			imputation	modified composite	COVID-19 pandemic: non- response imputation	policy	COVID-19 pandemic: MI assuming MAR within treatment group and occurrence of IEs Related to the COVID-19 pandemic: MI assuming MAR within treatment group
AUC of HECSI-90 from baseline up to Week 24	AUC (derived from binary)				Related to the COVID-19 pandemic: MI assuming MAR within treatment group		
Change in HECSI score from baseline to Week 24	Continuous	Composite	WOCF (including	Pandemic modified	Independent of the COVID-19 pandemic:	Treatment policy	Independent of the COVID-19 pandemic: MI
Change in HESD itch score (weekly average) from baseline to Week 12			baseline value)	composite	WOCF (including baseline value) Related to the COVID-19		assuming MAR within treatment group and occurrence of IEs
Change in HESD pain score (weekly average) from baseline to Week 12					pandemic: MI assuming MAR within treatment group		Related to the COVID-19 pandemic: MI assuming MAR within treatment group
AUC of change from baseline in DLQI score up to Week 24	AUC (derived from continuous)						

AUC=area under the curve; COVID-19=coronavirus disease 2019; DLQI=Dermatology Life Quality Index; HECSI=Hand Eczema Severity Index; HECSI-90=at least 90% improvement in HECSI from baseline; HESD=Hand Eczema Symptom Diary $^{\odot}$; IE=intercurrent event; IGA-CHE=Investigator's Global Assessment for chronic hand eczema $^{\odot}$; IGA-CHE TS=IGA-CHE treatment success, i.e. an IGA-CHE score of 0 (clear) or 1 (almost clear) with a \geq 2 step improvement from baseline; MAR=missing at random; MI=multiple imputation; TS=treatment success; WOCF=worst observation carried forward (including baseline value).

9.3.9 Exploratory Endpoints Analysis

The analysis of exploratory endpoints will be based on the FAS.

The analysis of exploratory endpoints will resemble the primary analysis for the primary estimand related to a specific endpoint type: binary, continuous, or AUC. For details refer to Section 9.3.6.

Table 9-4 provides an overview of the statistical analysis of the exploratory endpoints.

Table 9-4 Overview of the Statistical Analysis of Exploratory Endpoints

Endpoints	Type of	Primary estimand					
	endpoint	Strategy to handle IEs	Handling of missing data and data collected after IE				
Effica	асу						
IGA-CHE TS at Week 24.	Binary	Composite	Non-response imputation				
HECSI-75 at Week 12 and Week 24.							
HECSI-90 at Week 24.							
Reduction of HESD itch score (weekly average) of ≥3 points ¹ at Week 12 and Week 24.							
Reduction of HESD itch score (weekly average) of ≥4 points ² at Week 12 and Week 24.							
Reduction of HESD pain score (weekly average) of \geq 3 points ³ at Week 12 and Week 24.							
Reduction of HESD pain score (weekly average) of ≥4 points ⁴ at Week 12 and Week 24.							
Reduction of HESD score (weekly average) of ≥3 points ⁵ at Week 12 and Week 24.							
Reduction of HESD score (weekly average) of ≥4 points ⁶ at Week 12 and Week 24.							
Change in HESD itch score (weekly average) from baseline to Week 24.	Continuous	Composite	WOCF (including baseline value)				
Change in HESD pain score (weekly average) from baseline to Week 24.							
Change in HESD score (weekly average) from baseline to Week 12 and Week 24.							
AUC from baseline to Week 24 of reduction of HESD itch score (weekly average) of ≥3 points ¹	AUC (derived	Composite	Non-response imputation				
AUC from baseline to Week 24 of reduction of HESD itch score (weekly average) of ≥4 points ²	from binary)						
AUC from baseline to Week 24 of reduction of HESD pain score (weekly average) of ≥3 points ³							
AUC from baseline to Week 24 of reduction of HESD pain score (weekly average) of ≥4 points ⁴							
Health-related quality of life							
Change in DLQI score from baseline to Week 12 and Week 24.	Continuous	Composite	WOCF (including baseline value)				
Change in HEIS (individual domains and total score) from baseline to Week 12 and Week 24.							
Change in EQ-5D-5L index score from baseline to Week 12 and Week 24.							
Change in EQ-5D-5L visual analogue scale score from baseline to Week 12 and Week 24.							

Endpoints	Type of	Primary estimand		
	endpoint	Strategy to handle IEs	Handling of missing data and data collected after IE	
Reduction of DLQI score of ≥4 points ⁷ at Week 12 and Week 24.	Binary	Composite	Non-response imputation	
DLQI score of 0 or 1 at Week 12 and Week 24.				
Treatment satisfaction a	nd work prod	luctivity		
Change in WPAI-CHE (each individual domain) score from baseline to Week 12 and Week 24.	Continuous	Composite	WOCF (including baseline value)	
TSQM at Week 12 and at Week 24.			WOCF	

- 1. Among participants with a baseline HESD itch score (weekly average) ≥ 3 points.
- 2. Among participants with a baseline HESD itch score (weekly average) ≥4 points.
- 3. Among participants with a baseline HESD pain score (weekly average) \geq 3 points.
- 4. Among participants with a baseline HESD pain score (weekly average) ≥4 points.
- 5. Among participants with a baseline HESD score (weekly average) \geq 3 points.
- 6. Among participants with a baseline HESD score (weekly average) ≥4 points.
- 7. Among participants with a baseline DLQI score ≥4 points.

Abbreviations: AE=adverse event; ALT=alanine aminotransferase; AST=aspartate aminotransferase; CHE=chronic hand eczema; DLQI=Dermatology Life Quality Index; EQ-5D-5L=EuroQol 5-Dimension Health Questionnaire 5 Level; HECSI=Hand Eczema Severity Index; HECSI-75=at least 75% improvement in HECSI score from baseline; HECSI-90=at least 90% improvement in HECSI score from baseline; HEIS=Hand Eczema Impact Scale©; HESD=Hand Eczema Symptom Diary©; IGA-CHE=Investigator's Global Assessment for chronic hand eczema©; IGA-CHE TS=IGA-CHE treatment success; SAE=serious adverse event; TSQM=Treatment Satisfaction Questionnaire for Medicine; ULN=upper limit of normal; WOCF=Worst Observation Carried Forward; WPAI-CHE=Work Productivity and Activity Impairment – Chronic Hand Eczema.

9.3.10 Analysis of PGI-S and PGI-C

The 3 PGI-S scores (Itch PGI-S, Pain PGI-S, and HESD PGI-S) and the 3 PGI-C scores (Itch PGI-C, Pain PGI-C, and HESD PGI-C) will be summarised by visit for each treatment group.

9.3.11 Safety Analyses

All safety analyses will be made on the safety analysis set.

9.3.11.1 Adverse Events

AEs will be coded during the course of the trial according to the Medical Dictionary for Regulatory Activities (MedDRA). AEs will be presented by preferred term and primary system organ class (SOC).

Treatment-emergent AEs will be summarised; however, all AEs recorded during the course of the trial will be included in participant data listings. An event will be considered

treatment-emergent if it started after the first administration of IMP or if it started before the first administration of IMP and worsened in severity after the first administration of IMP. The tabulations described in the following will only include the treatment-emergent AEs. In each of the tabulations, AEs are defined by MedDRA preferred terms within primary SOC.

AEs will be summarised in terms of the number of participants with at least 1 event, the percentage of participants with at least 1 event, the number of events, and the event rate per 100 patient years of observation time.

Related AEs are defined as AEs for which the investigator has not described the causal relationship to the IMP as 'not related'.

An overall summary presenting any treatment-emergent AEs, deaths, SAEs, permanent discontinuations from IMP and/or withdrawals from the trial due to AEs, treatment-related AEs, and severe AEs will be presented.

Tabulations by SOC and preferred term will be presented for all AEs, SAEs, related AEs, AESIs, AEs leading to withdrawal from trial and AEs leading to permanent discontinuation of IMP. In addition, all AEs will be presented by severity and causal relationship to IMP, respectively. If an AE worsens in severity, the severity will be reported as the most severe recording for that AE.

SAEs will be evaluated separately, and a narrative will be given.

AESIs will be listed by treatment group. No narratives will be given.

AEs leading to withdrawal from trial and AEs leading to permanent discontinuation of IMP will be listed. The detailed listing will provide an overview of the individual cases and include the age and sex of the participant, treatment received at the time of AE onset, the AE preferred and reported terms, causality and severity of the AE, the action taken with the IMP, AE outcome, start and stop date of AE, duration of AE, and number of days since first and last IMP administration. No narratives will be given.

Specific summaries presenting AEs of hypertriglyceridaemia, hypercholesterolaemia, headache, liver toxicity will be prepared. The MedDRA search terms for these AEs will provided in the SAP.

Other events (medication error, misuse, and abuse of IMP) will be tabulated and listed. No narratives will be given.

9.3.11.2 Vital Signs and Physical Examination

For vital signs (resting blood pressure, pulse, and body temperature), the absolute values at baseline and EOT/ET as well as the change from baseline to EOT/ET will be summarised for each treatment group.

9.3.11.3 Clinical Laboratory Evaluation

For laboratory parameters, the absolute values as well as the changes from baseline will be summarised by visit for each treatment group.

A shift table will be produced for relevant parameters showing the categories at baseline against those at each post-baseline visit.

For participants with post-baseline values, the number of events reported up to Week 26 will be summarised. For the following laboratory abnormalities endpoints, binary estimand strategy will be applied, as described in Section 9.3.6.3:

- Increased levels of triglycerides >3.42 mmol/L (fasted state).
- Increased levels of cholesterol >7.75 mmol/L (fasted state).
- Increased levels of ALT and/or AST >3×ULN (or >3×baseline if baseline was abnormal but <2×ULN).
- Increased levels of ALP > 2.5 × ULN.
- Increased levels of bilirubin >1.5×ULN up to Week 26.

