9.3.6 Estimand Strategy

9.3.6.1 General Considerations

The analysis of endpoints related to efficacy and health-related quality of life will be based on the FAS.

The following primary and supplementary estimands will be defined for binary, continuous, and AUC endpoints (primary and key secondary endpoints):

- The primary estimand will use a 'composite' strategy to handle IEs. With a 'composite' strategy, the occurrence of an IEs is a component of the endpoint. The occurrence of any IE will lead to assume failure of the randomised treatment. For continuous endpoints, observed data after the IEs will be imputed as non-response by using WOCF (including baseline value) which is considered an extremely unfavourable value.
- A first supplementary estimand will use a 'pandemic modified composite' strategy. The strategy follows a 'composite' strategy for IEs independent of the COVID-19 pandemic. However, data collected after the IE related to the COVID-19 pandemic will be 'treated as missing' and imputed assuming MAR.
- A second supplementary estimand will use a 'treatment policy' strategy which attempts to quantify the effect of the randomised treatment, ignoring the occurrence of IEs. This policy reflects the intention-to-treat (ITT) principle and is intended to measure the effectiveness of the treatment under conditions closer to 'real world' conditions where patients will not adhere perfectly to the protocol when taking medication. Data collected for the endpoint of interest are used regardless of whether an IE occurred, except for the occurrence permanent discontinuation of IMP related to the COVID-19 pandemic data which will be assumed MAR and imputed.

To support the 'treatment policy' strategy, participants who experience IEs prior to Week 12 will be asked to attend the primary endpoint visit at Week 12 and nominal visit at Week 24 for collection of data. Participants who experience IEs between Week 12 and Week 24 will be asked to attend the nominal visit at Week 24 for collection of data.

For primary and key secondary endpoints only, pre-specified sensitivity analyses will also be conducted for selected combinations of endpoints and estimands to assess the robustness of the results with respect to the handling of missing data.

Analysis to summarise and assess the effect of patterns of missing data related to the COVID-19 pandemic will be specified in the SAP prior to DBL.

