The following IEs are considered to affect the interpretation of the estimated treatment effects:

- Initiation of rescue treatment: This IE occurs when a participant initiates rescue treatment. This IE can occur at the discretion of the investigator. If rescue treatment is initiated, regardless of relatedness to the COVID-19 pandemic, the participant must stop treatment with the IMP immediately and will not be allowed to restart treatment with the IMP (refer to Sections 6.8.2 and 7.1 for details). This IE is handled without assessing relatedness to the COVID-19 pandemic.
- **Permanent discontinuation of IMP independent of the COVID-19 pandemic:** This IE occurs when a participant permanently discontinues the IMP independent of the COVID-19 pandemic. This IE can occur at the participant's own initiative, at the discretion of the investigator or the sponsor, or if the participant is lost to follow-up.
- **Permanent discontinuation of IMP related to the COVID-19 pandemic**: This IE occurs when a participant permanently discontinues the IMP due to circumstances related to the COVID-19 pandemic; not attributed to lack of efficacy or randomised treatment features considered unacceptable by the participant.

The occurrence of IEs will be listed and summarised by treatment group. Table 9-2 presents an overview of how observed and missing data will be handled according to the IEs for the primary analysis for estimands.

Table 9-2 Handling of Observed and Missing Data According to the Intercurrent Events for the Primary Analysis for Estimands

		Estimand strategy for binary endpoints			Estimand strategy for continuous endpoints			
Intercurrent event	Data observed or missing	Composite (Primary)	Pandemic modified composite (First supplementary)	Treatment policy (Second supplementary)	Composite (Primary)	Pandemic modified composite (First supplementary)	Treatment policy (Second supplementary)	
Initiation of rescue treatment	Observed	Non-response	Non-response	Value will be used as observed	WOCF	WOCF	Value will be used as observed	
	Missing	Non-response	Non-response	MI (MAR)	WOCF	WOCF	MI (MAR)	
Permanent discontinuation of	Observed	Non-response	Non-response	Value will be used as observed	WOCF	WOCF	Value will be used as observed	
IMP independent of the COVID-19 pandemic	Missing	Non-response	Non-response	MI (MAR)	WOCF	WOCF	MI (MAR)	
Permanent	Observed	Non-response	MI (MAR)	MI (MAR)	WOCF	MI (MAR)	MI (MAR)	

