9.3.6.3 Estimand Strategy for Binary Endpoints

The population level summary will be the difference in response rates between delgocitinib cream and alitretinoin capsules.

The difference in response rates between the 2 treatment groups with the 95% CI will be calculated using the Cochran-Mantel-Haenszel (CMH) test stratified by region and hyperkeratotic/non-hyperkeratotic subtype.

When analyses require MI procedures of data, 100 complete datasets will be sampled. For each dataset, the difference in response rates will be analysed using the CMH test stratified by region and hyperkeratotic/non-hyperkeratotic subtype. The results of the analyses will be combined using Rubin's rule to provide the estimated treatment difference and associated standard error, and the 95% CI for the treatment difference will be calculated.

Primary Estimand: 'Composite' Strategy

For the primary analysis, observed data and missing data will be handled according to the IEs, as described in Table 9-2.

For the sensitivity analysis, which is rather conservative against the delgocitinib group, missing data at the endpoint of interest for participants who did not experience IEs prior to that will be handled as follows:

- For participants in the delgocitinib cream group, missing data will be imputed as non-response.
- For participants in the alitretinoin capsules group, missing data will be imputed using MI (100 iterations) assuming MAR. Binary response/non-response will be determined after imputation of the original raw continuous values when binary variable is obtained by derivation (e.g. for the HECSI-90 from baseline up to Week 24, the percentage of reduction from baseline will be derived from imputed values).

First Supplementary Estimand: 'Pandemic Modified Composite' Strategy

Observed data and missing data will be handled according to the IEs, as described in Table 9-2.

All missing or 'treated as missing' data will be imputed using MI assuming MAR within treatment groups. Once the 100 complete data sets have been generated by MI, non-responder imputation of relevant data points not affected by the COVID-19 pandemic will be applied.

Second Supplementary Estimand: 'Treatment Policy' Strategy

For the primary analysis, observed data and missing data will be handled according to the IEs, as described in Table 9-2.

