Missing data at Week 12 and Week 24 independent of the COVID-19 pandemic will be imputed using MI assuming MAR within 4 groups defined according to treatment group and whether the participant has experienced an IE (independent of the COVID-19 pandemic).

Missing data or 'treated as missing' data at Week 12 and Week 24 due to the COVID-19 pandemic will be imputed using MI assuming MAR within treatment group using data from participants who have not experienced an IE.

For the sensitivity analysis, missing data at Week 12 and Week 24 will be imputed as non-response, unless data is missing or 'treated as missing' due to the COVID-19 pandemic in which case it will be imputed using MI assuming MAR within treatment group using data from participants who have not experienced an IE.

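### Five exploratory laboratory-abnormality endpoints are sent to the efficacy responder rule, which replaces post-discontinuation and missing results with a 'non-response' that has no defined direction for a harm

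*Combined protocol and SAP*

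**What the plan says.** Section 9.3.11.3 first plans a summary of the number of events up to Week 26 among participants with post-baseline values. It then adds, for five threshold exceedances: "For the following laboratory abnormalities endpoints, binary estimand strategy will be applied, as described in Section 9.3.6.3".

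Section 9.3.6.3 gives the target of that strategy: "The population level summary will be the difference in response rates between delgocitinib cream and alitretinoin capsules". For the primary (composite) estimand it says: "For the primary analysis, observed data and missing data will be handled according to the IEs, as described in Table 9-2". In the composite column for binary endpoints, Table 9-2 assigns non-response to observed and missing data after rescue treatment or permanent discontinuation of IMP, whether or not related to COVID-19. It does the same for missing data without any intercurrent event.

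Section 9.3.11.3 does not name an estimand. Section 9.3.9 supplies a default: "The analysis of exploratory endpoints will resemble the primary analysis for the primary estimand related to a specific endpoint type". That points to composite, although Table 9-4 does not list the laboratory endpoints. Table 3-2 defines these endpoints as numbers of events up to Week 26, under an exploratory objective of comparing safety.

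**The concern.** Response and non-response have a clear meaning for HECSI-90 or IGA-CHE treatment success. For triglycerides above 3.42 mmol/L they do not, and no section supplies one. Section 9.3.6.1 treats an intercurrent event as failure of the randomised treatment. For a harm, that could be read as abnormality present. The opposite reading, that a responder is someone with the abnormality, makes non-response mean abnormality absent. Two programmers following the text could produce different risk differences from the same data.

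Neither reading gives a valid safety comparison. One discards abnormalities that were measured. The other counts as abnormal a participant who stopped for any reason, such as headache or lack of efficacy, on all five endpoints at once. Discontinuation is also not unrelated to the endpoints: Section 7.1 requires it for defined liver abnormalities in both arms, and for lipids that cannot be controlled in the alitretinoin arm.

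**Working it through.** **Plan's own figure.** None is stated for these endpoints. The only sample-size figure concerns the primary endpoint (Section 9.5): difference 7.5, SD 30, one-sided 2.5%, 80% power. The formula 2 × (1.960 + 0.842)² × (30/7.5)² gives 252 per arm, 504 in total. The planned 255 per arm gives 80.6% power. This reproduces, but it bears on the present point only through the arm size.

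**Which results are affected.** Table 1-1 schedules chemistry and lipids at early termination and at the follow-up visit 2 weeks after the last dose. It schedules none at the Week 12 primary endpoint visit or the nominal Week 24 visit for participants who have discontinued. So the observed results open to replacement are those at early termination, follow-up and any unscheduled sample.

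**Inputs for the illustrations.** n = 255 per arm (Section 9.5), taken as all having a post-baseline value. All event and discontinuation rates are assumptions, because the documents give none. Differences are alitretinoin minus delgocitinib, with an unstratified Wald 95% CI, SE = √[p₁(1−p₁)/n + p₂(1−p₂)/n].

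**A. Non-response = abnormality present.** The true exceedance rate is 5% in everyone, so the true difference is 0. With discontinuation rate d, coded rate = d + (1−d) × 0.05.

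| d, delgocitinib / alitretinoin | Coded rates | Coded difference, points (95% CI) |
|---|---|---|
| 10% / 10% | 14.5% / 14.5% | 0 |
| 10% / 12% | 14.5% / 16.4% | 1.9 (−4.4 to 8.2) |
| 10% / 15% | 14.5% / 19.25% | 4.8 (−1.7 to 11.2) |
| 10% / 20% | 14.5% / 24.0% | 9.5 (2.7 to 16.3) |
| 20% / 10% | 24.0% / 14.5% | −9.5 |

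The spurious difference is 0.95 times the difference in discontinuation, in whichever direction that goes.

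**B. Non-response = abnormality absent, exceedances before the intercurrent event kept.** Discontinuation is 10% versus 20%. A share b of discontinuers first exceed the threshold after stopping. True rate = 0.05 + d × b; coded rate = 0.05 in both arms, so the coded difference is always 0.

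| b, delgocitinib / alitretinoin | True rates | True difference lost, points |
|---|---|---|
| 5% / 5% | 5.5% / 6.0% | 0.5 |
| 10% / 10% | 6.0% / 7.0% | 1.0 |
| 5% / 15% | 5.5% / 8.0% | 2.5 (−1.9 to 6.9) |

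**C. A true difference exists.** Take 5/255 versus 20/255 with an exceedance (2.0% versus 7.8%, 5.9 points), unrelated to discontinuation, which is 10% versus 20%.
- Present coding: (5×0.9 + 25.5)/255 = 11.8% and (20×0.8 + 51)/255 = 26.3%, difference 14.5 points.
- Absent coding, with every exceedance in a discontinuer lost (harsher than B): 4.5/255 = 1.8% and 16/255 = 6.3%, difference 4.5 points.
- With discontinuation at 10% in both arms, both codings give 5.3 points. Equal rates create no spurious difference but still shrink a real one.

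**The case against.** Much of the case on the other side stands and limits the point.

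- **An observed count is already planned.** A reader might infer that the trial has no straightforward summary of observed exceedances. The sentence before the quoted one in Section 9.3.11.3 provides an event count. The gap lies within Section 9.3.6.3, where every option uses non-response imputation, multiple imputation or both, and none is an observed proportion.
- **The analysis set is settled.** Section 9.3.9 says "The analysis of exploratory endpoints will be based on the FAS", which might suggest a conflict. Section 9.2 assigns safety endpoints to the safety analysis set, and Section 9.3.11 repeats this for all safety analyses. The FAS sentence is loose wording.
- **Treatment policy is not assigned here.** Section 9.3.6.3 says under that strategy "Missing data at Week 12 and Week 24 independent of the COVID-19 pandemic will be imputed using MI assuming MAR within 4 groups", and a reader might object that no laboratory sample is scheduled at those visits after discontinuation. But the synopsis and Table 3-1 attach the supplementary estimands to primary and key secondary endpoints, and treatment policy to Week 12 and Week 24 endpoints. These laboratory endpoints are neither.
- **Earlier exceedances are probably kept.** The column headings in Tables 9-3 and 9-4 limit the primary-estimand handling to missing data and data collected after the intercurrent event. An abnormality that triggers discontinuation normally precedes it. It is therefore too strong to say that absent coding would erase the liver or lipid signals that led to stopping.
- **The SAP may define the coding.** Section 9 leaves technical detail to the SAP, and the combined document contains no separate SAP text on this. The protocol wording would still direct these endpoints to Table 9-2.

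None of this gives non-response a direction for a harm, or stops Table 9-2 from replacing measured post-discontinuation values.

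**Conclusion.** The point holds and is minor. As written, the default rule for five exploratory safety endpoints replaces post-event results and missing values with an undefined category, and neither reading of that category yields a valid between-arm safety comparison. Absent coding does little damage: at most 2.5 points in illustration B, with few samples affected. Present coding can do much more: 9.5 points from a true zero in illustration A at 10% versus 20% discontinuation.

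A reader might take 9.5 points as the expected bias. The documents do not support that. Every rate is assumed, the large figure needs both present coding and unequal discontinuation, and the sign depends on which arm discontinues more. The actual size is unknown. The event count, by-visit values and changes, shift tables and all confirmatory tests are unaffected.

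**What to change.** Delete the reference to the data handling of Section 9.3.6.3 for these five endpoints and replace it with the following:

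- **Population:** safety analysis set, participants with a post-baseline value.
- **Event:** at least one observed post-baseline value above the threshold up to Week 26, regardless of intercurrent events, with no non-response or multiple imputation. State whether unscheduled samples count.
- **Reporting:** n (%), number of events, and the Cochran-Mantel-Haenszel risk difference stratified by region and subtype with 95% CI. Alongside, give events per 100 patient-years of observation, as Section 9.3.11.1 does for AEs, because observation time may differ between arms.

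State the downside: in the proportion, unsampled time after early discontinuation counts as event-free. Naming the estimand and the direction of non-response would remove the ambiguity but not the distortion.

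The cost is one paragraph of protocol or SAP wording before database lock and simpler programming. No new data, visits or participants are needed.
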